#### 5.1.2 Subject Inclusion Criteria

In order to be eligible for participation in this trial, the subject must:

- Be willing and able to provide written informed consent/assent for the trial.
- Be  $\geq 18$  years of age on day of signing informed consent.

- Have measurable disease based on RECIST 1.1.
- Have a performance status of 0 or 1 on the ECOG Performance Scale.
- Demonstrate adequate organ function as defined in Table 1.

Table 1 Adequate Organ Function Laboratory Values

System	Laboratory Value
Hematological	
Absolute neutrophil count (ANC)	$\geq 1,500$ /mcL
Platelets	$\geq 100,000$ / mcL
Hemoglobin	$\geq 9$ g/dL or $\geq 5.6$ mmol/L without transfusion or EPO dependency (within 7 days of assessment)
Renal	
Serum creatinine OR Measured or calculated a creatinine clearance (GFR can also be used in place of creatinine or CrCl)	$\leq 1.5$ X upper limit of normal (ULN) OR $\geq 60$ mL/min for subject with creatinine levels $> 1.5$ X institutional ULN
Hepatic	
Serum total bilirubin	$\leq 1.5$ X ULN OR Direct bilirubin $\leq$ ULN for subjects with total bilirubin levels $> 1.5$ X ULN
AST (SGOT) and ALT (SGPT)	$\leq 2.5$ X ULN OR $\leq 5$ X ULN for subjects with liver metastases (only in the phase II portion)
Albumin	$\geq 2.5$ mg/dL
Coagulation	
International Normalized Ratio (INR) or Prothrombin Time (PT)	$\leq 1.5$ X ULN unless subject is receiving anticoagulant therapy as long as PT or PTT is within therapeutic range of intended use of anticoagulants
Activated Partial Thromboplastin Time (aPTT)	$\leq 1.5$ X ULN unless subject is receiving anticoagulant therapy as long as PT or PTT is within therapeutic range of intended use of anticoagulants
a Creatinine clearance should be calculated per institutional standard.	

- Female subject of childbearing potential should have a negative urine or serum pregnancy within 72 hours prior to receiving the first dose of study medication. If the urine test is positive or cannot be confirmed as negative, a serum pregnancy test will be required.
- Female subjects of childbearing potential (Section 5.7.2) must be willing to use an adequate method of contraception as outlined in Section 5.7.2 – Contraception, for the course of the study through 120 days after the last dose of study medication.

Note: Abstinence is acceptable if this is the usual lifestyle and preferred contraception for the subject.

- Male subjects of childbearing potential (Section 5.7.1) must agree to use an adequate method of contraception as outlined in Section 5.7.1- Contraception, starting with the first dose of study therapy through 120 days after the last dose of study therapy.

Note: Abstinence is acceptable if this is the usual lifestyle and preferred contraception for the subject.

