#### **5.3.1 Pembrolizumab**

Adverse events (both non-serious and serious) associated with pembrolizumab exposure may represent an immunologic etiology. These adverse events may occur shortly after the first dose or several months after the last dose of treatment. Pembrolizumab must be withheld for drug-related toxicities and severe or life-threatening AEs as per 3 below. See Section 5.6 for supportive care guidelines, including use of corticosteroids.

Toxicities unrelated to pembrolizumab will not ordinarily result in the modification of pembrolizumab dose. AEs will be defined based on the National Cancer Institute (NCI) Common Terminology Criteria for Adverse Events (CTCAE) version 4.

Table 3 Dose Modification Guidelines for Drug-Related Adverse Events

General instructions:				

 
1. Corticosteroid taper should be initiated upon AE improving to Grade 1 or less and continue to taper over at least 4 weeks.
 
2. For situations where pembrolizumab has been withheld, pembrolizumab can be resumed after AE has been reduced to Grade 1 or 0 and corticosteroid has been tapered. Pembrolizumab should be permanently discontinued if AE does not resolve within 12 weeks of last dose or corticosteroids cannot be reduced to <math>\leq 10</math> mg prednisone or equivalent per day within 12 weeks.
 
3. For severe and life-threatening irAEs, IV corticosteroid should be initiated first followed by oral steroid. Other immunosuppressive treatment should be initiated if irAEs cannot be controlled by corticosteroids.
 
				
Immune-related AEs	Toxicity grade or conditions (CTCAEv4.0)	Action taken to pembrolizumab	irAE management with corticosteroid and/or other therapies	Monitor and follow-up
Pneumonitis	Grade 2	Withhold	
 
• Administer corticosteroids (initial dose of 1-2 mg/kg prednisone or equivalent) followed by taper
 
	
 
• Monitor participants for signs and symptoms of pneumonitis
 
• Evaluate participants with suspected pneumonitis with radiographic imaging and initiate corticosteroid treatment
 
• Add prophylactic antibiotics for opportunistic infections
 

	Grade 3 or 4, or recurrent Grade 2	Permanently discontinue		

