Diarrhea / Colitis	Grade 2 or 3	Withhold	
 
• Administer corticosteroids (initial dose of 1-2 mg/kg prednisone or equivalent) followed by taper
 
	
 
• Monitor participants for signs and symptoms of enterocolitis (ie, diarrhea, abdominal pain, blood or mucus in stool with or without fever) and of bowel perforation (ie, peritoneal signs and ileus).
 
• Participants with <math>\geq</math> Grade 2 diarrhea suspecting colitis should consider GI consultation and performing endoscopy to rule out colitis.
 
• Participants with diarrhea/colitis should be advised to drink liberal quantities of clear fluids. If sufficient oral fluid intake is not feasible, fluid and electrolytes should be substituted via IV infusion.
 

	Grade 4	Permanently discontinue		

AST / ALT elevation or Increased bilirubin	Grade 2	Withhold	
 
Administer corticosteroids (initial dose of 0.5- 1 mg/kg prednisone or equivalent) followed by taper
 
	
 
Monitor with liver function tests (consider weekly or more frequently until liver enzyme value returned to baseline or is stable)
 

	Grade 3 or 4	Permanently discontinue	
 
Administer corticosteroids (initial dose of 1-2 mg/kg prednisone or equivalent) followed by taper
 
	
Type 1 diabetes mellitus (T1DM) or Hyperglycemia	Newly onset T1DM or Grade 3 or 4 hyperglycemia associated with evidence of $\beta$ -cell failure	Withhold	
 
Initiate insulin replacement therapy for participants with T1DM
 
Administer anti-hyperglycemic in participants with hyperglycemia
 
	
 
Monitor participants for hyperglycemia or other signs and symptoms of diabetes.
 

Hypophysitis	Grade 2	Withhold	
 
Administer corticosteroids and initiate hormonal replacements as clinically indicated.
 
	
 
Monitor for signs and symptoms of hypophysitis (including hypopituitarism and adrenal insufficiency)
 

	Grade 3 or 4	Withhold or permanently discontinue 		

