#### **B. Hepatotoxicity**

Liver Function Test Abnormalities Transaminase elevations have been reported in study XL888-001. Four subjects (12.1%) experienced AEs of AST increased (all Grade 3) and two subjects (6.1%) with ALT increased (both Grade 2). Bilirubin elevation (one Grade 3, one Grade 2) were also seen. Increases in ALP, ALT, AST, SDH, and GGT present in both rat and dog preclinical studies following XL888 administration, consistent with potential hepatotoxicity of this agent. Subjects on XL888 should have liver function tests at baseline and at regular intervals while on treatment.

XL888 will be interrupted for rising transaminases as follows:

1. Transaminase increase to  $> 5 \times \text{ULN}$  [upper limit of normal] in subjects with levels less than  $2.5 \times \text{ULN}$  at baseline
2. Doubling of transaminase level for those subjects with elevated baseline transaminases (levels equal or greater than  $2.5 \times \text{ULN}$ )
3. Isolated elevations of total bilirubin ( $>2\text{XULN}$ ) without other explanation.

Subjects with XL888-related transaminase elevations will have weekly monitoring of transaminases. XL888 will be resumed after transaminases return to baseline and patients will have a dose reduction.

XL888 should be discontinued if hepatic dysfunction is not reversed despite interruption of study treatment for 3 weeks.

Elevations  $>3 \times$  ULN of ALT or AST concurrent with  $>2 \times$  ULN total bilirubin without other explanation can indicate drug induced liver injury and drug should be permanently discontinued.

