#### **8.6.1.2 Laboratory Data**

Descriptive statistics for worst grade of each laboratory parameter by the NCI CTCAE scale version 4.0 at baseline and follow-up will be presented along with change from Baseline. Additionally, laboratory values  $\geq$  Grade 3 severity will be tabulated and listed on an individual subject basis.

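### Patients with liver metastases may enter with AST/ALT up to 5x ULN, but the pembrolizumab, XL888 and laboratory-reporting rules handle an elevated baseline inconsistently and need reconciling

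*Combined protocol and SAP*

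**What the plan says.** **Entry.** In Table 1 of 5.1.2 the AST/ALT limit is 2.5x ULN, or 5 "X ULN for subjects with liver metastases (only in the phase II portion"). No part of the trial carries that label; its parts are a dose escalation and an expansion.

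**Pembrolizumab.** In Table 3 of 5.3.1, the row "AST / ALT elevation or Increased bilirubin" withholds at Grade 2 and permanently discontinues at Grade 3 or 4. The only mention of baseline in that row concerns how long to monitor: "until liver enzyme value returned to baseline or is stable". Under the general instructions, "pembrolizumab can be resumed after AE has been reduced to Grade 1 or 0 and corticosteroid has been tapered". Discontinuation is permanent if the event has not resolved within 12 weeks of the last dose. The table is limited by its title, "Table 3 Dose Modification Guidelines for Drug-Related Adverse Events", and the text above it adds: "Toxicities unrelated to pembrolizumab will not ordinarily result in the modification of pembrolizumab dose".

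**XL888.** Section 5.3.2.2 B interrupts at more than 5x ULN if baseline was below 2.5x ULN. For a baseline at or above 2.5x ULN its trigger is "Doubling of transaminase level for those subjects with elevated baseline transaminases". The general rule in 5.3.2 delays XL888 for any Grade 3 non-hematologic toxicity. Its exceptions cover fatigue, nausea, vomiting and diarrhea, not transaminases. It accepts recovery to baseline or to Grade 1 or less.

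**Analysis.** Section 8.6.1.2 summarises the worst grade of each laboratory parameter at baseline and follow-up, with change from baseline. It then says that values at or above "Grade 3 severity will be tabulated and listed on an individual subject basis". That tabulation has no baseline or repeat-test condition.

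**The concern.** The entry criterion accepts an elevated transaminase as a feature of liver metastases. The rules that apply afterwards do not treat it consistently. Read literally, Table 3 can require a patient to fall below the level at which the trial admitted them before pembrolizumab restarts, with a permanent stop if that is not achieved in time. For XL888, one section measures the rise from the patient's own baseline and another uses the absolute grade.

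The expansion is meant to confirm the toxicity profile in pancreatic and colorectal cancer. For a patient who starts close to 5x ULN, a Grade 3 laboratory value may reflect the entry level and ordinary visit-to-visit variation rather than treatment. A crude count cannot separate the two, and investigators following different sections could handle the same patient differently.

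**Working it through.** **1. The plan's own figure.** The only Grade 3 transaminase rate in the documents is for AST in study XL888-001 (5.3.2.2 B): 4/33 = 12.1%, which reproduces. The documents give no within-patient variability and no expected number entering under the 5x ULN allowance.

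**2. Assumed grades.** Grade 2 is >3 to 5x ULN and Grade 3 is >5x ULN. The >5x ULN trigger in 5.3.2.2 B is consistent with this. The resumption conflict needs only that Grade 1 ends below 5x ULN. Closeness to the permanent-stop grade needs Grade 3 to start at about 5x ULN.

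**3. The rules side by side, for a patient entering at 4.5x ULN.**

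| Rule | Level at which it acts | As a change from entry |
|---|---|---|
| Table 3, Grade 2: withhold | >3x ULN | already met on level at entry |
| Table 3, Grade 3: permanent stop | >5x ULN | 5/4.5 = 1.11, a rise of 11% |
| Table 3, resume at Grade 0-1 | 3x ULN or lower | 1 - 3/4.5 = 33% below entry |
| 5.3.2, XL888 delay at Grade 3 | >5x ULN | a rise of 11% |
| 5.3.2.2 B, XL888 interruption | 2 x 4.5 = 9x ULN | a rise of 100% |

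The Table 3 rows apply only to events attributed to drug, and the XL888 guidelines only to toxicities attributed to XL888. For entry at 4x ULN, resumption needs a fall of 1 - 3/4 = 25% below entry.

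**4. Number of tests.** Chemistry is drawn on day 1 of each cycle and on days 8 and 15 of cycles 1 and 2 (7.1.4). After C1D1 that gives 8 draws through C5D1 and 12 through C9D1. Eight is used below.

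**5. Noise alone, one patient.** Take log-normal variation around a constant mean m, with s = sqrt(ln(1 + CV^2)). The chance that one test exceeds 5x ULN is p = 1 - Phi((ln(5/m) + s^2/2)/s). For m = 4.5 and CV 15%: s = 0.149, z = (0.105 + 0.011)/0.149 = 0.78 and p = 0.217. Over 8 independent tests, 1 - 0.783^8 = 0.86.

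**6. Noise alone, a population.** Means are uniform over the stated band, a patient is kept if the screening draw is at or below 5x ULN, and 8 later draws follow with no drug effect. The table gives the share with at least one value above 5x ULN.

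| Mean AST or ALT (assumed) | CV 10% | CV 15% | CV 20% | CV 25% |
|---|---|---|---|---|
| 3-5x ULN | 27% | 39% | 51% | 61% |
| 3-4x ULN | 1% | 10% | 24% | 39% |

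With 12 draws the first row becomes 31%, 45%, 59% and 70%.

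**7. Illustrative cohort size.** If 10% to 20% of the 32 expansion patients enter in this range (assumed), that is 3.2 to 6.4 patients. For 3-5x ULN: 3.2 x 0.27 = 0.9 to 6.4 x 0.61 = 3.9 patients. For 3-4x ULN: 3.2 x 0.01 = 0.03 to 6.4 x 0.39 = 2.5 patients.

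**8. Could the doubling criterion define the count?** In the 3-5x ULN model, add a true sustained 50% rise. Then 98% to 99% of patients have a value above 5x ULN. A count that also requires doubling from screening misses about 88%, 63%, 44% and 32% of patients at CV 10%, 15%, 20% and 25%.

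**The case against.** The strongest reply is that the plan already has safeguards:

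- Table 3 covers drug-related events only. Section 5.5.1 asks investigators to rule out causes such as metastatic disease. Section 7.2 counts a pre-existing condition as an adverse event only on clinically significant worsening, and exclusion 6 lets the investigator decline a patient whose laboratory abnormality would confuse interpretation.
- Section 8.6.1.2 presents baseline grade and change from baseline and lists Grade 3 values by subject, so an entry value near the limit would be visible in a small cohort.
- All analyses are descriptive.
- The noise figures depend on an assumed CV and an assumed spread of entry values.

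Much of this stands. A reader might infer that noise by itself produces Grade 3 hepatotoxicity or pembrolizumab stops. The documents do not support that: noise produces laboratory values, and action on pembrolizumab requires attribution. Protection is incomplete, because section 5.3 directs that events not clearly attributable to either agent lead to modification of both.

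A reader might also infer that one value leads to opposite actions for the two drugs. That is not established, since 5.3.2 delays XL888 at Grade 3 as well, and 5.3 permits independent modification when attribution is clear. What the text shows is that the two XL888 rules differ from each other.

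The safeguards do not remove the conflict over resumption, and they do not condition the Grade 3 laboratory tabulation, which requires no attribution. The separate baseline and follow-up summaries do not specify a cross-tabulation.

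**Conclusion.** The point holds as an inconsistency between the entry criterion and the rules that follow it, with a secondary reporting problem. On the assumed CTCAE cut-offs, an eligible patient can start in the withholding grade, and after a drug-attributed hold can be required to fall below the entry value to resume. The XL888 sections disagree on whether baseline matters.

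For the Grade 3 laboratory tabulation, noise alone would put about 27% to 61% of patients with a mean of 3-5x ULN above 5x ULN at least once, or 1% to 39% if means lie at 3-4x ULN. These ranges rest on CV 10% to 25%, independent errors, one enzyme, 8 draws and no drug effect. The number of patients affected is unknown.

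Two further readings should be resisted. The escalation DLTs are not affected by this allowance if, as presumed, the label means the expansion; asymptomatic Grade 3 laboratory abnormalities also need more than 21 days to count as a DLT. And the doubling criterion is not a sound definition of hepatotoxicity for analysis, because it would miss many patients with a real 50% rise.

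**What to change.** 1. Reconcile Table 1 (5.1.2), Table 3 and its general instructions (5.3.1), the general XL888 rule (5.3.2) and the XL888 hepatic rule (5.3.2.2 B) for patients admitted with elevated transaminases. Which clinical rule applies is for the sponsor to decide.
2. Replace the phase II label in Table 1 with the name of the phase meant.
3. In 8.6.1.2, keep the crude Grade 3 or higher count as the headline. Add a baseline-by-worst-grade shift table for AST and ALT, split the Grade 3 or higher count by baseline below versus at or above 2.5x ULN, and show fold-change from baseline. The doubling criterion may appear as a supplementary line only.

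The cost is a wording amendment and one extra table. The values are already collected, and the crude count stays available for comparison with other trials.

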### **5.1.3 Subject Exclusion Criteria**

The subject must be excluded from participating in the trial if the subject:

1. Is currently participating and receiving study therapy or has participated in a study of an investigational agent and received study therapy or used an investigational device within 4 weeks of the first dose of treatment.
2. Has a diagnosis of immunodeficiency or is receiving systemic steroid therapy or any other form of immunosuppressive therapy within 7 days prior to the first dose of trial treatment.
3. Has a known history of active TB (Bacillus Tuberculosis)
4. Hypersensitivity to pembrolizumab or history of severe allergic or hypersensitivity reactions to excipients (e.g., Polyethylene glycol [PEG] 300 and Polysorbate 80)
5. Clinically significant cardiovascular disease or peripheral vascular (e.g. myocardial infarction, unstable angina within 6 months of study entry), symptomatic congestive heart failure, serious uncontrolled cardiac arrhythmia requiring medications, baseline QTc > 450 msec or previous history of QT prolongation while taking other medications
6. Other medications, or severe acute/chronic medical or psychiatric condition, or laboratory abnormality that may increase the risk associated with study participation or study drug administration, or may interfere with the interpretation of study results, and in the judgment of the investigator would make the subject inappropriate for entry into this study
7. Has had a prior anti-cancer monoclonal antibody (mAb) within 4 weeks prior to study Day 1 or who has not recovered (i.e.,  $\leq$  Grade 1 or at baseline) from adverse events due to agents administered more than 4 weeks earlier.
8. Has had prior chemotherapy, targeted small molecule therapy, or radiation therapy within 2 weeks prior to study Day 1 or who has not recovered (i.e.,  $\leq$  Grade 1 or at baseline) from adverse events due to a previously administered agent.
  - Note: Subjects with  $\leq$  Grade 2 neuropathy are an exception to this criterion and may qualify for the study.

- Note: Major surgical procedure, or significant traumatic injury within 28 days of registration or incompletely healed surgical wounds are exclusions. Minor surgical procedures such as placement of central venous device (excluding PICC line) are allowed 7 days prior to enrollment to the study.
9. Has a known additional malignancy that is progressing or requires active treatment. Exceptions include basal cell carcinoma of the skin or squamous cell carcinoma of the skin that has undergone potentially curative therapy or in situ cervical cancer.
  10. Has known active central nervous system (CNS) metastases and/or carcinomatous meningitis. Subjects with previously treated brain metastases may participate provided they are stable (without evidence of progression by imaging for at least four weeks prior to the first dose of trial treatment and any neurologic symptoms have returned to baseline), have no evidence of new or enlarging brain metastases, and are not using steroids for at least 7 days prior to trial treatment. This exception does not include carcinomatous meningitis which is excluded regardless of clinical stability.
  11. Has active autoimmune disease that has required systemic treatment in the past 2 years (i.e. with use of disease modifying agents, corticosteroids or immunosuppressive drugs). Replacement therapy (eg., thyroxine, insulin, or physiologic corticosteroid replacement therapy for adrenal or pituitary insufficiency, etc.) is not considered a form of systemic treatment.
  12. Has known history of, or any evidence of active, non-infectious pneumonitis.
  13. Has an active infection requiring systemic therapy.
  14. Has known substance abuse disorders that would interfere with cooperation with the requirements of the trial.
  15. Is pregnant or breastfeeding, or expecting to conceive or father children within the projected duration of the trial, starting with the screening visit through 120 days after the last dose of trial treatment.
  16. Has received prior therapy with an anti-PD-1, anti-PD-L1, anti-PD-L2, or HSP inhibitor.
  17. Has a known history of Human Immunodeficiency Virus (HIV) (HIV 1/2 antibodies).
  18. Has known active Hepatitis B (e.g., HBsAg reactive) or Hepatitis C (e.g., HCV RNA [qualitative] is detected).
  19. History of malabsorption or other condition that would interfere with absorption of study drugs.

20. History of or evidence of retinal pathology on ophthalmologic examination that is considered a risk factor for neurosensory retinal detachment, RVO (retinal vein occlusion), or neovascular macular degeneration. The risk factors for RVO are listed below. Patients should be excluded if they have the following current conditions:

- a. Uncontrolled glaucoma with intra-ocular pressures > 21mmHg
- b. Serum cholesterol > Grade 2
- c. Hypertriglyceridemia > Grade 2
- d. Hyperglycemia (fasting) > Grade 2

21. Has received a live vaccine within 30 days of planned start of study therapy.

*Note: Seasonal influenza vaccines for injection are generally inactivated flu vaccines and are allowed; however intranasal influenza vaccines (e.g., Flu-Mist®) are live attenuated vaccines, and are not allowed.*

#### 5.1.4 Screen Failures

Minimal data for subjects who fail screening will be collected such as demographic information and the reason for screen failure. Such subjects may be re-screened at the discretion of the investigator after approval by the Data and Safety Monitoring Committee (DSMC). The reason for the need to re-screen a subject will be documented in the subject's source documents.

## 5.2 Trial Treatments

The treatment to be used in this trial is outlined below in Table 2

Table 2 Trial Treatment

Drug	Dose/Potency	Dose Frequency	Route of Administration	Regimen/Treatment Period
Pembrolizumab	200 mg	Q3W	IV infusion	Day 1 of each 3 week cycle
XL888	As Below	Twice weekly (Days 1 and 4)	Oral	Twice weekly (days 1 and 4) cycle is 3 weeks

